7.2 Missing Data Imputation

Missing pterygium hyperemia grading and pterygium characteristics data for Day 7 and Day 28 may be imputed using the last observation carried forward (LOCF) method from scheduled or unscheduled post-baseline visits.

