## 9. STATISTICAL METHODS AND DATA ANALYSES

### 9.1. GENERAL CONSIDERATION

A detailed SAP will be developed and finalized prior to the final database lock. Any deviations from the originally planned statistical analysis or SAP will be described and justified in the clinical study report. All statistical processing will be performed using the most current version of SAS® at the time of the analysis. Data listings will be provided for all baseline variables collected (subject disposition, all demographic and baseline characteristics, prior and concomitant medications, and study drug compliance), all efficacy outcomes, and all safety outcomes (deaths, AEs, clinical laboratory values, vital signs, physical examination). Individual data will be listed and sorted by treatment, subject ID, visit, and time point.

Summary statistics for continuous measurements will be reported using the number of study subjects with data values, mean, median, standard deviation (SD), minimum, and maximum. For continuous efficacy outcomes 95% confidence intervals will be provided.

Summary statistics for categorical variables will be reported using the number and percentage of study subjects within each level of the variable.

Medical history, concurrent therapies, and adverse events will be coded to MedDRA and WHO Drug dictionaries, as appropriate.

Baseline is defined as the last non-missing measurement prior to the initiation of investigational product. Change from baseline will be calculated as Visit – Baseline. Baseline measures are defined as the last non-missing measure prior to the initiation of investigational product. Change from baseline will be calculated as Visit – Baseline. All primary and secondary analyses will be two-sided at a significance level of 0.10.

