7.3 Efficacy Analyses

Efficacy analyses will be performed for both the mITT Analysis Set and the Per Protocol Analysis Set. All hypothesis testing will be two-sided at a significance level of 0.05, with the RMP-A03 vehicle treatment group designated as the reference group.

An error occurred whereby subjects were randomized based on incorrect strata. The sponsor acknowledges slightly imbalance of the number of subjects in randomized treatment across the strata; however, as this is a first-in-human study, it’s important to explore the impact of the actual baseline pterygium hyperemia grading category to the treatment effect on efficacy endpoints, so the analysis will emphasize using the correct baseline grading. As the baseline pterygium hyperemia grading in this study will either be [REDACTED], analysis models are thus proposed to adjust the actual baseline pterygium hyperemia grading as a continuous covariate, rather than the category used during stratification.

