7.3.1.1 Mixed Model with Repeated Measures (MMRM)

The treatment difference between the RMP-A03 and RMP-A03 vehicle treatment groups will be evaluated for the change from baseline pterygium hyperemia grading, with the RMP-A03 vehicle treatment group used as reference, using a MMRM. This analysis will use observed data for mITT Analysis Set.

The model will include terms for baseline pterygium hyperemia grading, treatment, visit, and the interaction of treatment and visit, with visit as a repeated measure and subject as random effect.

[REDACTED]

The least squares mean (LSM) and two-sided 95% confidence interval (CI) will be presented for treatment group, and visit. Additionally, the difference between each RMP-A03 treatment group and RMP-A03 vehicle treatment group will be calculated, along with the two-sided 95% CI.

The following is reference code for this analysis:

```
[REDACTED]
```

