7.3.1.2 Analysis of Covariance (ANCOVA)

An ANCOVA model will be used to evaluate the difference between the RMP-A03 and RMP-A03 vehicle treatment groups in change from baseline in pterygium hyperemia grading at each post-baseline visit. This analysis will use LOCF for the mITT Analysis Set, and observed data for PP Analysis Set.

The model will include terms for treatment, and actual baseline pterygium hyperemia grading [REDACTED] will be adjusted in the model as a continuous covariate. The LSM and two-sided 95% CI will be presented for each treatment group. Additionally, the difference between

each RMP-A03 dose level and RMP-A03 vehicle will be calculated, along with the two-sided 95% CI.

The following is reference code for this analysis:

A large black rectangular redaction box covering several lines of text, likely the reference code mentioned in the preceding sentence.

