9 POWER AND SAMPLE SIZE

For Stage 1, up to 5 subjects will be treated in each dose cohort for a total of up to 20 subjects. No formal sample size calculation was performed.

In Stage 2, approximately 25 subjects will be treated in each treatment arm for a total of approximately 75 subjects. The sample size calculation was as follows.

For the primary efficacy endpoint of change from baseline in pterygium hyperemia grading at Day 28, a sample size of 25 completed subjects per arm provides approximately 90% power to detect a 0.66 statistically significant difference between an active dose arm and the placebo at the 0.05 significance level. This assumes that the treatment difference between an active dose arm and the placebo is at least 0.66 and that the within-treatment standard deviation is approximately 0.7 for all three treatment arms.

The within-treatment standard deviation comes from the published results of the study in patients with pterygium. The expected treatment difference is conservatively estimated as the observed difference from the study minus one standard error.

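### The mITT ANCOVA of the primary endpoint uses loosely specified LOCF that normally substitutes a Day 7 grading for a missing Day 28 one, and the SAP does not rank it below the MMRM

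*SAP*

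**What the plan says.** Protocol section 9.6 leaves missing data to the SAP. SAP section 7.2 covers hyperemia grading and pterygium characteristics at Days 7 and 28 only; missing values there "may be imputed using the last observation carried forward (LOCF) method from scheduled or unscheduled post-baseline visits".

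SAP section 7.3.1.2 adds an ANCOVA of change in hyperemia grading at each post-baseline visit, which means Days 7, 28, 56 and 84. On the data it is definite: "This analysis will use LOCF for the mITT Analysis Set, and observed data for PP Analysis Set". The MMRM in section 7.3.1.1 is different: "This analysis will use observed data for mITT Analysis Set".

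Protocol section 9.8.1 names only the MMRM on the mITT set for the primary endpoint. The SAP gives neither model priority. Section 7.3.2 applies both to corneal encroachment and length and describes both as the models of the primary analysis. Section 8, which lists changes from the protocol, does not mention the ANCOVA.

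In SAP Table 2, pterygium is assessed at Days 7, 28, 56 and 84, and Day 14 is a phone call. A footnote asks sites to try to complete the exit procedures, which include the pterygium assessment, at early termination.

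**The concern.** LOCF assumes that nothing changes after the last grading. For a missing Day 28 value, the last scheduled grading was taken after one of four weeks of dosing. If the drug effect is still building at Day 7, the filled-in value understates it. If gradings drift in both arms and one arm has more missing data, the arms are shifted by different amounts and a difference can appear or disappear for that reason alone.

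The rule also has gaps:

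- Section 7.2 says LOCF *may* be used and section 7.3.1.2 says it will be, so the choice could still be made after the data are seen.
- Days 56 and 84 are in the ANCOVA but have no imputation rule.
- No scheduled post-baseline grading precedes Day 7, and baseline is not a permitted source.
- A subject first graded after dosing at Day 56 is in the mITT set but has nothing to carry to Day 28.

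At stake is a second estimate of the primary endpoint, on the same analysis set as the MMRM, that may disagree with it while the SAP does not say which one counts. The same applies to encroachment and length.

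**Working it through.** **Inputs from the documents.** For the effect, the SAP assumes that "the treatment difference between an active dose arm and the placebo is at least 0.66". It takes the SD of the change as 0.7 in every arm. It states that "a sample size of 25 completed subjects per arm provides approximately 90% power", and section 7.3 sets the level: "All hypothesis testing will be two-sided at a significance level of 0.05". (Protocol section 9.1 says instead "All primary and secondary analyses will be two-sided at a significance level of 0.10". That is a separate discrepancy.)

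**The plan's own figure.** Noncentrality = 0.66 / (0.7 × √(2/25)) = 0.66 / 0.198 = 3.33. A two-sample t-test with 48 df at two-sided 0.05 has power 90.4% (normal approximation 91.5%). The stated 90% reproduces at 0.05; at 0.10 it would be 95.0%. LOCF plays no part in this calculation.

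**Inputs the documents do not give, so assumed.**

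- m, the fraction missing at Day 28: 4% to 20%, or 1 to 5 of 25. The plan counts 25 completers per arm and also treats about 25 per arm, so it makes no allowance.
- f, the Day 7 effect as a fraction of the Day 28 effect: 0 to 1.
- Missingness is unrelated to outcome within arm, and Day 7 is the value carried.

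**Formula.** Under LOCF, each arm mean = (1 − m) × Day 28 mean + m × Day 7 mean. With equal m in the two arms, any common drift cancels and the difference is 0.66 × (1 − m(1 − f)).

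| m, both arms | f = 0 | f = 0.5 | f = 1 |
|---|---|---|---|
| 4% | 0.634 | 0.647 | 0.660 |
| 10% | 0.594 | 0.627 | 0.660 |
| 20% | 0.528 | 0.594 | 0.660 |

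Example: 0.66 × (1 − 0.20 × 0.5) = 0.594, or −10%. The range is 0 to −20%. By the same formula, an effect that peaked early and then faded (f above 1) would be overstated.

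**Unequal missingness.** Assume vehicle changes by −0.1 at Day 7 and −0.3 at Day 28, with f = 0.5. Active is then −0.1 − 0.33 = −0.43 and −0.3 − 0.66 = −0.96. Differences are vehicle minus active.

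- 20% missing in active only: active = 0.8 × (−0.96) + 0.2 × (−0.43) = −0.854; difference −0.3 + 0.854 = 0.554.
- 20% missing in vehicle only: vehicle = 0.8 × (−0.3) + 0.2 × (−0.1) = −0.26; difference −0.26 + 0.96 = 0.700.

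A steeper case: Day 7 difference 0.2, with a drift of −0.3 in both arms by Day 28.

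- 25% missing in active, 10% in vehicle: active = 0.75 × (−0.96) + 0.25 × (−0.2) = −0.77; vehicle = 0.9 × (−0.3) = −0.27; difference 0.50.
- Percentages swapped: active = 0.9 × (−0.96) + 0.1 × (−0.2) = −0.884; vehicle = 0.75 × (−0.3) = −0.225; difference 0.659, almost no bias.

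No true effect, drift −0.4, with 20% missing in one arm and none in the other: 0.8 × (−0.4) = −0.32 against −0.40, a spurious difference of 0.08.

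**Comparison with a likelihood estimate.** In 6,000 simulated trials (25 per arm, two visits, SD 0.7, assumed correlation 0.6, f = 0.5), LOCF averaged 0.627 at 10% missing and 0.593 at 20%. A likelihood estimate under missing at random, the principle behind the MMRM, averaged 0.659 and 0.661.

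**The case against.** The strongest reply is that the primary analysis does not use LOCF. The protocol names the MMRM, the SAP runs it on observed data, and the per-protocol ANCOVA also uses observed data. This stands: a reader might infer that the primary result is biased, and the documents do not support that. It does not settle the matter, because the SAP nowhere makes the ANCOVA secondary to the MMRM.

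A reader might also infer that LOCF cannot operate at Day 7. That is too strong. Section 7.2 admits unscheduled post-baseline visits, so a grading before Day 7 can be carried if one exists; other subjects stay missing.

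Nor is bias certain. It is zero when the full effect is present at Day 7 and missingness is equal. At 4% missing and f = 0.5 it is only −2%. The fall to 0.50 needs the heavier missingness to be in the active arm. Early-termination gradings, where obtained, may be later than Day 7 and closer to the truth than the two-visit calculation assumes. All of this stands and makes the size conditional.

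Lower power should not be charged to LOCF. In a simulation with 20% missing, f = 0.5 and correlation 0.5, power was 83.5% with LOCF and 83.9% with the likelihood estimate. Almost all the fall from 90% comes from the missing data.

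Finally, in a first-in-human study whose primary objective is safety, tidier wording might seem enough. Wording would close the gaps in the rule, but it would leave an estimator that can err in either direction when a better one is cheap.

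**Conclusion.** The concern holds for the mITT ANCOVA of hyperemia grading, and for the same analysis of encroachment and length. It does not extend to the protocol's primary MMRM. LOCF at Day 28 will normally carry a Day 7 value, the rule is optional in one section and definite in another, and Days 56 and 84 are not covered.

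The bias depends on two quantities the documents do not state. Over the assumed ranges with equal missingness, it runs from none to a 20% understatement of the 0.66 difference. With unequal missingness and drift it can go either way, so LOCF cannot be defended as reliably conservative. These figures assume missingness unrelated to outcome within arm and no later unscheduled or early-termination grading. The change should be made before unmasking; it does not put the primary analysis in doubt.

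**What to change.** 1. In SAP section 7.3, name the MMRM on the mITT set as the primary analysis and the ANCOVA as a sensitivity analysis, and say the same for encroachment and length in section 7.3.2. List the ANCOVA in section 8 as an addition to the protocol.
2. Delete LOCF from sections 7.2 and 7.3.1.2.
3. Either drop the mITT ANCOVA, since the MMRM already handles missing data under missing at random, or run it on data multiply imputed under missing at random from treatment, baseline and all observed visits. State that this covers Days 7, 28, 56 and 84.
4. If departures from missing at random are to be examined, specify a delta-adjusted or vehicle-based imputation and fix its details before unmasking.

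The cost is SAP wording, a little programming, and somewhat wider intervals than single imputation gives. No visit, assessment or sample size changes.

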7.3 Efficacy Analyses

Efficacy analyses will be performed for both the mITT Analysis Set and the Per Protocol Analysis Set. All hypothesis testing will be two-sided at a significance level of 0.05, with the RMP-A03 vehicle treatment group designated as the reference group.

An error occurred whereby subjects were randomized based on incorrect strata. The sponsor acknowledges slightly imbalance of the number of subjects in randomized treatment across the strata; however, as this is a first-in-human study, it’s important to explore the impact of the actual baseline pterygium hyperemia grading category to the treatment effect on efficacy endpoints, so the analysis will emphasize using the correct baseline grading. As the baseline pterygium hyperemia grading in this study will either be [REDACTED], analysis models are thus proposed to adjust the actual baseline pterygium hyperemia grading as a continuous covariate, rather than the category used during stratification.

7.3.1 Pterygium Hyperemia Grading Analysis

To evaluate the primary and exploratory efficacy endpoints, change from baseline in pterygium hyperemia grading at Day 28, and Day 56 and Day 84, respectively, baseline, post-baseline, and change from baseline values for pterygium hyperemia grading in the study eye will be summarized by treatment group and visit.

7.3.1.1 Mixed Model with Repeated Measures (MMRM)

The treatment difference between the RMP-A03 and RMP-A03 vehicle treatment groups will be evaluated for the change from baseline pterygium hyperemia grading, with the RMP-A03 vehicle treatment group used as reference, using a MMRM. This analysis will use observed data for mITT Analysis Set.

The model will include terms for baseline pterygium hyperemia grading, treatment, visit, and the interaction of treatment and visit, with visit as a repeated measure and subject as random effect.

[REDACTED]

The least squares mean (LSM) and two-sided 95% confidence interval (CI) will be presented for treatment group, and visit. Additionally, the difference between each RMP-A03 treatment group and RMP-A03 vehicle treatment group will be calculated, along with the two-sided 95% CI.

The following is reference code for this analysis:

```
[REDACTED]
```

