## **9.8.EFFICACY ANALYSIS**

### **9.8.1. PRIMARY EFFICACY ANALYSES**

The primary efficacy endpoint will evaluate change from baseline in pterygium hyperemia grading at Day 28. Summaries of pterygium hyperemia grading will be provided by visit and by treatment group. The primary endpoint of change from baseline in pterygium hyperemia grading at Day 28 will be analyzed by a mixed-effects model with repeated measures (MMRM) using all the data collected post-baseline for the mITT Population. The MMRM model will include model terms treatment, visit, treatment-by-visit interaction, baseline pterygium grading, and baseline pterygium hyperemia grading category used for stratification [REDACTED]. Each dose will be compared with the placebo arm at the 0.05 significance level at each visit. The least squares mean (LSM) for each treatment arm will be calculated together with its 95% confidence interval. In addition, the difference between each active treatment and the placebo will also be calculated together with its 95% confidence interval.

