Escalation to the next dose cohort will only occur after the 7-day safety data for all subjects in the preceding cohort has been reviewed and upon confirmation of no safety concerns.

3.1.2 Stage 2

Stage 2 will initiate upon completion of Stage 1 and following determination of MTD among the 4 evaluated doses. Stage 2 is a randomized, doubled-masked, placebo-controlled study comparing the efficacy and safety of RMP-A03 with placebo in patients with pterygium. Approximately 75 patients are planned to be randomized to 1 of 3 treatment groups in a 1:1:1 ratio. These treatment groups will consist of the 2 doses of RMP-A03 and the RMP-A03 vehicle. A single eye drop of RMP-A03 or RMP-A03 vehicle will be applied TID to the study eye for a total of 28 days. Patients will be followed for a total of 84 days. The study will consist of 7 visits as follows: Screening (up to 60 days prior to the baseline visit), Baseline/Day 1, Day 7, Day 14 (Phone Visit), Day 28, Day 56, and Day 84 (see Table 1-2 for study visits and procedures and Figure 1 for the study schematic).

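### As listed, the MMRM uses one baseline slope for all four visits, so the Day 28 difference may be slightly mis-adjusted; a baseline-by-visit term is a cheap safeguard

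*SAP*

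**What the plan says.** **Model terms.** SAP 7.3.1.1 states: "The model will include terms for baseline pterygium hyperemia grading, treatment, visit, and the interaction of treatment and visit". Protocol 9.8.1 has the same structure, "The MMRM model will include model terms treatment, visit, treatment-by-visit interaction, baseline pterygium grading", plus the stratification category, which the SAP drops (SAP 7.3 and 8). Neither list contains a baseline-by-visit interaction. The text directly after the SAP's model sentence and the reference code are redacted, so the coded model cannot be checked from the public documents.

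**Visits in the model.** The protocol runs the MMRM "using all the data collected post-baseline for the mITT Population". SAP 3.1.2 places the visits after baseline at "Day 7, Day 14 (Phone Visit), Day 28, Day 56, and Day 84", and SAP Table 2 schedules pterygium assessments at all of these except the phone call. Study drug "will be applied TID to the study eye for a total of 28 days". Four visits therefore feed the model, and Days 56 and 84 are off drug.

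**Why the adjustment carries weight.** SAP 7.3 reports that subjects were randomized on incorrect strata: "The sponsor acknowledges slightly imbalance of the number of subjects in randomized treatment across the strata". It gives no size or direction. Its answer is that the models will "adjust the actual baseline pterygium hyperemia grading as a continuous covariate, rather than the category used during stratification".

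**Companion analysis.** SAP 7.3.1.2 plans an ANCOVA at each post-baseline visit, adjusted for actual baseline grade. It uses LOCF in the mITT set and observed data in the per-protocol set.

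**The concern.** With baseline as a main effect only, the model assumes that baseline grade relates to change in the same way early on drug, at the end of dosing, and four and eight weeks after dosing stops. The fitted slope is a weighted average over those visits and need not be the Day 28 slope. No section gives a reason for expecting a constant slope.

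With intact stratification this would matter little, because the arms would be close at baseline and the size of the slope would hardly affect the contrast. Here the stratification went wrong, and the SAP relies on covariate adjustment to deal with it. If adjustment is the remedy, it should be able to fit the primary time point. At stake is a possible shift in the estimated Day 28 difference between a dose and vehicle, in a direction that depends on which arm has the higher baseline grades.

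**Working it through.** **Inputs from the documents.** 25 completed subjects per arm, difference 0.66, SD 0.7, two-sided 0.05 (SAP 7.3 and 9); three arms, 1:1:1 (SAP 3.1.2); four assessed visits.

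**Inputs assumed, because the documents give none.** Baseline slopes by visit; correlation between visits (compound symmetry 0.5 or AR(1) 0.6); two baseline grades one unit apart; imbalance of 1 to 5 of 25 subjects shifted by one grade, that is 1/25 = 0.04 to 5/25 = 0.20 grade in the arm means.

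**1. The plan's own figure.** SE of a difference = 0.7 × √(2/25) = 0.198. Then 0.66/0.198 = 3.33, and Φ(3.33 − 1.96) = 91.5%. With the t distribution on 48 df it is 90.4%. The stated power of about 90% reproduces. The 95% CI half-width is about 0.40.

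**2. The error formula.** Let b₂₈ be the true Day 28 slope and Δ the difference between two arms in mean baseline grade. The raw Day 28 difference has expectation τ₂₈ + b₂₈Δ. With complete data the common-slope MMRM subtracts b_c·Δ, where b_c = 1′Σ⁻¹b / 1′Σ⁻¹1. So

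error at Day 28 = (b₂₈ − b_c) × Δ.

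The visit weights in b_c are 0.25 each under compound symmetry, and 0.36, 0.14, 0.14, 0.36 under AR(1) 0.6. A Day 28 slope of its own removes the error.

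**3. Numbers put in.** Slopes are for Days 7, 28, 56 and 84.

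| Assumed slopes | b_c | b₂₈ − b_c | Error for Δ = 0.04 to 0.20 |
|---|---|---|---|
| −0.5 at every visit | −0.5 | 0 | 0 |
| −0.3, −0.4, −0.5, −0.6 (mild drift) | −0.45 | 0.05 | 0.002 to 0.010 |
| −0.2, −0.4, −0.6, −0.8 (strong drift) | −0.50 | 0.10 | 0.004 to 0.020 |
| −0.4, −0.3, −0.6, −0.6 (Day 28 set apart) | −0.475 to −0.486 | 0.175 to 0.186 | 0.007 to 0.037 |
| −0.6, −0.1, −0.6, −0.6 (extreme) | −0.475 to −0.529 | 0.375 to 0.429 | 0.015 to 0.086 |

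The largest non-extreme value, 0.037, is 0.037/0.66 = 6% of the planned difference and 0.037/0.198 = 0.19 SE. The largest extreme value, 0.086, is 13% of 0.66 and 0.43 SE. A different extreme pattern (−0.2, −0.6, −0.2, 0, correlation 0.5, with 10 vs 16 of 25 at the higher grade) has b_c = −0.25 and a gap of −0.35. With |Δ| = 6/25 = 0.24, the error is 0.35 × 0.24 = 0.084 in size.

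**4. Simulation check.** 3 × 25 subjects, four visits, SD 0.7, AR(1) 0.6, estimated unstructured covariance, complete data, 4000 runs per scenario.

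- With a visit-specific slope, bias was at most 0.006 in every scenario.
- In the extreme case with 5 of 25 shifted unfavourably, common-slope bias was 0.090, power was 0.78 against about 0.90, and type I error was 0.059.
- Under strong drift with 5 of 25 shifted, common-slope bias was 0.024 against 0.076 for the unadjusted difference. In the extreme case the common slope did worse than no adjustment: 0.090 against 0.015.
- With constant slopes and 5 of 25 shifted, the SD of the estimate was 0.201 (common slope) against 0.202 (visit-specific). A smaller simulation (700 runs per scenario, visit correlation 0.5) put the SE increase at 0.005 at most.

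**The case against.** The case for leaving the model alone has several parts.

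- **The harm needs two conditions, and neither is documented.** No visit slopes and no baseline means by arm are given. This stands, and it limits the point to a possibility.
- **The admitted imbalance is only slight.** SAP 7.3 speaks of "slightly imbalance of the number of subjects in randomized treatment across the strata", which concerns counts, not mean baseline grade. This also stands. If true grade had been left wholly unstratified with half the subjects at each level (an assumption), a gap of 10 or more of 25 between two arms would occur in about 0.7% of comparisons, so calculations on that scale do not illustrate a slight imbalance. A gap of 5 or more would occur in about 20%, so the upper end of the range used here is not far-fetched. Partly correct stratification would lower both figures.
- **Slopes may be similar across visits.** The outcome is change from baseline, so measurement error in the shared baseline puts a similar negative component into every visit's slope. This makes the extreme patterns less plausible but does not establish a constant slope.
- **A visit-specific slope is already planned in the ANCOVA.** True, and a material discrepancy would show beside the MMRM. But the ANCOVA changes the missing-data handling or the population at the same time. No observed-data mITT analysis has its own Day 28 slope, and any disagreement with the MMRM could come from either source.
- **Efficacy is a secondary objective of a first-in-human study, and a common slope is a legitimate, parsimonious choice.** This supports low severity. It does not argue against a term that costs almost nothing.
- **The redacted code may already contain the term.** Possible. If so, only the list of model terms needs completing.

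**Conclusion.** The point holds as a low-severity improvement. The model as listed shares one baseline slope across four visits, two of them off drug, in a trial that relies on baseline adjustment after a stratification error. The Day 28 difference may therefore be mis-adjusted by (Day 28 slope minus common slope) × (baseline difference). Under assumed mild to strong drift with 1 to 5 of 25 subjects shifted by one grade, that is about 0.002 to 0.04 grade, up to about 6% of 0.66 and 0.19 SE. It reaches about 0.08 to 0.09 only under extreme assumptions, and is zero if slopes are constant or arms are balanced. All of these figures rest on assumed slopes, covariance and imbalance, and on complete data.

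A reader might infer that the Day 28 difference is in fact adjusted by the wrong amount, or that the SAP concedes a difference in mean baseline grade. The documents support neither reading: they report a slight imbalance in numbers across strata, and they say nothing about slopes or baseline means. Over the mild to strong range the planned adjustment also brings the estimate closer to the truth than no adjustment would.

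**What to change.** First check whether the redacted MMRM code already contains the interaction. If it does, add it to the terms listed in SAP 7.3.1.1. If not, add baseline hyperemia grading × visit to the MMRM, or state why a common slope is expected.

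Carry the same structure into the MMRMs for corneal encroachment and length in SAP 7.3.2. That section uses the primary models, and SAP 8 names hyperemia grading as the covariate for all efficacy endpoints, so state which baseline value enters those models and let its slope vary by visit.

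The cost is one model term, one sentence in the SAP, three degrees of freedom (four visit slopes instead of one), and an SE increase of at most about 0.005 if slopes are truly constant.
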